4.1.1 Length of the Study

The total duration of the study for each participant will be approximately 16 weeks divided as follows:

- Screening: Up to 8 weeks
- In clinic period: Days -2 to 10
- Final follow-up: Day 57 ± 4

4.1.2 Treatment Groups

The following tentative dose levels are planned:

- Dose level 1: 0.1 mg/kg RO7126209 or matching placebo
- Dose level 2: 0.3 mg/kg RO7126209 or matching placebo
- Dose level 3: 0.9 mg/kg RO7126209 or matching placebo
- Dose level 4: 2.7 mg/kg RO7126209 or matching placebo
- Dose level 5: 5.4 mg/kg RO7126209 or matching placebo

The dose levels are tentative, and may be revised based on emerging data. Higher doses than planned may be administered provided that all the dose escalation increments and stopping rules are followed. [REDACTED]

[REDACTED] with a maximum of 60 participants enrolled in the study.

If the safety data (AEs, ECGs, vital signs, laboratory safety tests, [REDACTED] assessments) of the first 48 hours following intravenous administration of RO7126209 or placebo is acceptable based on the judgment of the Investigator, the remaining participants will be dosed [REDACTED] after the first dosing occasion.

4.1.3 Dose Escalation Decision Criteria

The decision to escalate to the next dose level will be made jointly by the Sponsor study team, the Investigator and any other person the Investigator or Clinical Pharmacologist considers necessary to assist with the decision (Section 4.1.4 and Section 4.1.5).

Dose decisions (to escalate, reduce, or repeat) between cohorts will be made following review of all available cumulative (i.e., including emergent data from all previous cohorts) safety data (including AEs, laboratory safety test results, safety biomarkers, ECGs, vital signs, [REDACTED] assessments) collected [REDACTED]

[REDACTED]

[REDACTED]

[REDACTED]

The starting dose will be 0.1 mg/kg. Study treatment will be adaptive in nature. Doses may be repeated, adjusted downwards, or intermediate doses may be investigated based on safety, tolerability and PK data at each dose level, as well as on model-based prediction of the anticipated maximum DLE rate.

4.1.4 Stopping Rules Criteria

4.1.4.1 General Study Stopping Rules

[REDACTED]

[REDACTED]

[REDACTED]

4.1.4.2 Stopping Rules after Sentinel Cohort

[REDACTED]

[REDACTED]

[REDACTED]

[Redacted text]

4.1.4.3 Dose Escalation Stopping Rules

[Redacted text]

- [Redacted text]
- [Redacted text]
- [Redacted text]
- [Redacted text]
- [Redacted text]
- [Redacted text]
- [Redacted text]
- [Redacted text]
- [Redacted text]

In case dose escalation is stopped, lower doses within the tolerated dose range could be investigated or a dose repeated in subsequent cohorts (or additional participants added), in order to increase the amount of data within the tolerated dose range.

On the basis of the safety and tolerability profile and observed PK, the number of participants at the next dose level may be revised or a dose level may be expanded.

Due to the exploratory nature of this clinical study, its conduct can be discontinued at any time at the discretion of the Sponsor. This will not constitute a premature termination of the study.

4.1.5 Communication Strategy

A safety review team will provide dose recommendations for all cohorts of the study. The representatives of the safety review team will be from Clinical Pharmacology, Biometrics, Safety Science, Clinical Science, and Operations together with the Investigator(s) and the Project lead of the CRO (and any other the Investigator or Clinical Pharmacologist considers necessary to assist with the decision).

There will be an ongoing review of available data (see Section 4.1.3) prior to dosing remaining participants of a dose group after evaluation of the sentinel cohort and initiation of the next dose. A Dose Escalation Meeting will be conducted between the Sponsor study team and Investigator prior to dosing of the next dose level.

[REDACTED]

- [REDACTED]

- [REDACTED]

- [REDACTED]

- [REDACTED]

[REDACTED]

- [REDACTED]

- [REDACTED]

In addition to these communications, the Sponsor and investigators will be in regular contact throughout the study by email/telephone/fax, as per normal interactions during the conduct of a clinical study, and the Sponsor will arrange regular teleconferences and meetings to discuss study status.

The Sponsor will be available 24 hours a day to discuss any medical or study-related issues that may arise during the conduct of this study.

Additional details for communication strategy and dose-escalation procedure can be found in the separate Medical Data Review Plan.

4.2 SCIENTIFIC RATIONALE FOR STUDY DESIGN

The study rationale is provided in Section [2.1](#).

4.2.1 Rationale for Study Population

The study will be conducted in healthy male participants aged 18 to 40 years (inclusive).

The healthy volunteer population has been selected to minimize the risk of ARIA. ARIA-E (edema) and ARIA-H (microhemorrhages) are common side effects of monoclonal antibodies targeting fibrillar forms of amyloid beta. As the main objective of this study is the characterization of the general safety and tolerability profile, immunogenicity and pharmacokinetics of RO7126209, the absence of confounding diseases in healthy volunteers allows for a clearer and more consistent assessment of the main objectives. In addition, healthy volunteers are unlikely to require concomitant medications which could impact PK and safety parameters.

In line with the above paragraph the age range has been limited to 40 years to reduce the risk of amyloid plaque in the brain. According to a recent publication ([Pletnikova 2018](#)) the risk of occurrence of diffuse amyloid plaque in the study population is low.

4.2.2 Rationale for Control Group

This study is designed to be adequate and well-controlled. Participants will be randomized to RO7126209 or placebo treatment. The randomization scheme to active and placebo groups is considered necessary to generate an adequate within study comparator dataset to allow proper evaluation of the magnitude of any treatment effects. The study is Investigator/participant-blind to eliminate potential bias.

4.2.3 Rationale for Biomarker Assessments

[REDACTED]

4.2.4 Rationale for CSF Sampling

CSF samples will be taken to monitor safety and to measure RO7126209 concentrations.

[REDACTED]

4.3 DOSE JUSTIFICATION

4.3.1 Justification for Starting Dose

The starting dose of RO7126209 is proposed to be 0.1 mg/kg IV. The planned starting dose was selected based on the nonclinical findings, relevant regulatory guidelines ([EMA 2015](#), [FDA 2005](#)) and clinical experience with gantenerumab, the A β targeting entity in RO7126209.

A starting dose of 6 mg/kg RO7126209 was initially calculated based on the NOAEL [REDACTED] and on the recommendations provided in the FDA guidance, using body weight conversion (following the recommendation for IV administered proteins for proteins of molecular weight > 100 kDa), of a 10-fold safety factor between human equivalent dose (HED) and maximum recommended starting dose (MRSD). Given the estimated pharmacologically active systemic exposure described below, the MRSD level is predicted to show potential therapeutic activity. Thus the starting dose was lowered to 0.1 mg/kg, based on a comparison of projected brain concentrations (using the translational PKPD model) and clinical experience from gantenerumab. Details for the estimation of the therapeutic dose range for RO7126209 and considerations for the safety of the proposed starting dose are given below.

For the selection of a potential pharmacologically active dose range for RO7126209 a translational PKPD model was developed, incorporating preclinical information on brain penetration in NHPs from both RO7126209 and gantenerumab, and an internally developed PKPD model from gantenerumab (see [RO7126209 IB](#)).

[REDACTED]

1.6 - 3 mg/kg.

[REDACTED]

Monoclonal antibodies targeting fibrillar forms of amyloid beta like gantenerumab may be associated with the occurrence of ARIAs. The gantenerumab target dose of 510 mg SC Q2W is administered only after an up-titration period of 9 months to mitigate incidence and severity of ARIAs. As this side effect is also expected to occur before reaching the target dose of RO7126209, the starting dose has been lowered to reach brain exposures similar to gantenerumab doses that have not been associated with ARIAs in patients with AD.

[REDACTED]

0.1 mg/kg

[REDACTED]

The population selected for BP41192, healthy young male volunteers, is not expected to experience ARIAs due to lack of fibrillar forms of amyloid beta in the brain. However, clinical experience with gantenerumab and the potential for ARIA findings have been taken into account in order to characterize the general safety and tolerability profile and PK of the dose range which is likely to be tested in future studies in Alzheimer's Disease patients.

Safety Margins

The safety margins associated with the starting dose based on the preclinical toxicokinetic data, and estimated NOAEL in the 2-week GLP toxicology study and projected human PK are provided in [Table 4](#) below. Note that, taking a conservative approach, the high exposure scenario was used for the calculation of the safety margins.

If safety allows, the highest dose to be tested in the SAD will be selected so that the

[REDACTED]

[REDACTED]

[REDACTED]

[REDACTED]	[REDACTED]	[REDACTED]	[REDACTED]
[REDACTED]	[REDACTED]	[REDACTED]	[REDACTED]
0.1	[REDACTED]	[REDACTED]	[REDACTED]

[REDACTED]

[REDACTED]

0.1 mg/kg

In conclusion the non- clinical data and the PKPD translational model that draws upon gantenerumab clinical data support a starting dose of 0.1 mg/kg IV for RO7126209.

4.3.2 Justification for Dose Escalation

With a starting dose of 0.1 mg/kg, the dose expected to reach similar brain concentration as 400 mg gantenerumab IV, which was well tolerated in the single ascending dose study in AD patients (BN18726), will be reached after the second dose escalation step (0.9 mg/kg).

[REDACTED]

(2.7 mg/kg).

1.6 to 3 mg/kg

2.7 mg/kg

5.4 mg/kg).

5.4 mg/kg

[REDACTED]

5.4 mg/kg.

Table 5 Tentative Dose Escalation

[REDACTED]	[REDACTED]	[REDACTED]	[REDACTED]	[REDACTED]	[REDACTED]
	[REDACTED]	[REDACTED]	[REDACTED]	[REDACTED]	[REDACTED]
0.1	[REDACTED]	[REDACTED]	[REDACTED]	[REDACTED]	[REDACTED]
0.3	[REDACTED]	[REDACTED]	[REDACTED]	[REDACTED]	[REDACTED]
0.9	[REDACTED]	[REDACTED]	[REDACTED]	[REDACTED]	[REDACTED]
2.7	[REDACTED]	[REDACTED]	[REDACTED]	[REDACTED]	[REDACTED]
5.4	[REDACTED]	[REDACTED]	[REDACTED]	[REDACTED]	[REDACTED]

[REDACTED]

4.4 END OF STUDY DEFINITION

The end of the study is defined as the date when the last participant last observation (LPLO) occurs. LPLO is expected to occur 57 ± 4 days after last dose administration.

5. STUDY POPULATION

The study population rationale is provided in Section [4.2.1](#).

The participants in this study will be healthy male volunteers, between 18 and 40 years of age, inclusive, who fulfill all of the given inclusion criteria.

Prospective approval of protocol deviations from recruitment and enrollment criteria, also known as protocol waivers or exemptions, is not permitted.

5.1 INCLUSION CRITERIA

Participants are eligible to be included in the study only if all of the following criteria apply:

Informed Consent

1. [REDACTED]

Age

2. [REDACTED]

Type of Participants

3. Healthy status is defined by the absence of evidence of any active or chronic disease following a detailed medical and surgical history, a complete physical examination including vital signs, 12-lead ECG, ophthalmologic examination, hematology, blood chemistry, coagulation, serology, and urinalysis.
4. [REDACTED]

Weight

5. BMI of 18-30 kg/m² inclusive

Sex

6. Male participants

During the treatment period (from dosing on Day 1) and until the final follow-up visit (Day 57 ± 4 days), agreement to:

- Remain abstinent (refrain from heterosexual intercourse) or use contraceptive measures such as a condom plus an additional contraceptive method that together result in a failure rate of < 1% per year, with a partner who is a woman of childbearing potential (WOCBP, as defined in Section 1 of [Appendix 5](#)).
- With pregnant female partner, remain abstinent (refrain from heterosexual intercourse) or use contraceptive measures such as a condom to avoid exposing the embryo.
- Refrain from donating sperm from Day 1 of the study until 90 days after last dose.

[REDACTED]

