8.3.5 Pregnancy

Male participants will be instructed through the Informed Consent Form to immediately inform the Investigator if their partner becomes pregnant during the study or within 57 ± 4 days after dosing.

If a pregnancy is reported, the Investigator should inform the Sponsor within 24 hours of learning of the pregnancy and should follow the pregnancy reporting process as detailed in [Appendix 5](#).

Abnormal pregnancy outcomes (e.g., spontaneous abortion, fetal death, stillbirth, congenital anomalies, ectopic pregnancy) are considered SAEs ([Appendix 5](#)).

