8.10.4 Assessments at Study Completion/Early Termination Visit

Participants who complete the study or discontinue from the study early (as described in Section 4.1.4 and Section 7) will be asked to return to the clinic 57 ± 4 days after the dose of study drug for a follow-up visit (see Section 1.3 and Section 8.10.5).

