2 COLLECTION OF PREGNANCY INFORMATION

- **Male participants with partners who become pregnant**

The Investigator will attempt to collect pregnancy information on any male participant's female partner who becomes pregnant while the male participant is in this study (see Section 8.3.5 Pregnancy). This applies only to male participants who receive study treatment.

Attempts should be made to collect and report details of the course and outcome of any pregnancy in the partner of a male participant exposed to study treatment. The

Investigator will record pregnancy information on the Clinical Trial Pregnancy Reporting Form and submit it to the Sponsor within 24 hours of learning of the partner's pregnancy. When permitted by the site, the pregnant partner would need to sign an Authorization for Use and Disclosure of Pregnancy Health Information to allow for follow-up on her pregnancy. If the authorization has been signed, the Investigator should update the Clinical Trial Pregnancy Reporting Form with additional information on the course and outcome of the pregnancy when available. An Investigator who is contacted by the male participant or his pregnant partner may provide information on the risks of the pregnancy and the possible effects on the fetus, to support an informed decision in cooperation with the treating physician and/or obstetrician. The female partner will be followed to determine the outcome of the pregnancy. Information on the status of the mother and child will be forwarded to the Sponsor. Monitoring of the participant's partner should continue until conclusion of the pregnancy. Any termination of the pregnancy will be reported regardless of fetal status (presence or absence of anomalies) or indication for procedure.

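### Criterion 6 ends contraception 30–38 days before its own sperm-donation limit, and partner-pregnancy reporting also stops short of 90 days, at least for the last cohort

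*Combined protocol and SAP*

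**What the plan says.** Criterion 6 appears in the synopsis and in Section 5.1. Its opening sentence fixes the period of the undertakings: "During the treatment period (from dosing on Day 1) and until the final follow-up visit", given as Day 57 ± 4. Three bullets follow.

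- **Partner able to conceive:** abstinence, or a condom plus a second method. The bullet has no end date of its own.
- **Pregnant partner:** abstinence, or "use contraceptive measures such as a condom to avoid exposing the embryo". Again there is no separate end date.
- **Sperm donation:** "Refrain from donating sperm from Day 1 of the study until 90 days after last dose". This bullet has its own start and end.

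Section 8.3.5 has men instructed, through the consent form, to tell the Investigator "if their partner becomes pregnant during the study or within 57 ± 4 days after dosing". In Appendix 5, Section 2, the first paragraph covers a partner "who becomes pregnant while the male participant is in this study". The second paragraph asks for attempts to report "any pregnancy in the partner of a male participant exposed to study treatment", without a time limit.

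Two other sections bear on the dates. Section 8.10.4 says participants "will be asked to return to the clinic 57 ± 4 days after the dose of study drug for a follow-up visit". Section 4.4 defines the end of the study by the last participant's last observation and adds that "LPLO is expected to occur 57 ± 4 days after last dose administration".

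**The concern.** The sponsor judges 90 days to be the right precaution for donated sperm, yet lets a participant conceive with a partner, or expose an existing pregnancy, about a month sooner. A reason for keeping sperm out of donation for 90 days would ordinarily apply to conception by intercourse as well. No readable text separates the two.

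The reporting rule makes the gap harder to see. A man whose partner conceives between the final visit and day 90 may have no instruction to tell anyone. This is a first-in-human study in men aged 18 to 40 who expect no therapeutic benefit, so early information on partner pregnancies has some value. What is at stake is protection of partners and embryos, and safety capture. Endpoints, dose escalation and analysis are not affected.

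**Working it through.** The plan states no figure for this gap, so there is none to reproduce. The check is calendar arithmetic.

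**Inputs**
- One IV dose per participant (Section 4.1), given on Day 1 (Figure 1). The last dose is therefore the Day 1 dose.
- Table 1 puts Day 1 at 0 h and Day 8 at 168 h, so study day d is d − 1 days after dosing.
- Final visit: Day 57 ± 4, that is Day 53 to Day 61.
- Donation limit: 90 days after the dose, which is Day 91.

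**Contraception against donation**

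Gap = 90 − (visit day − 1).

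| Visit | Days after dose | Gap to 90 days |
|---|---|---|
| Day 53 | 52 | 38 |
| Day 57 | 56 | 34 |
| Day 61 | 60 | 30 |

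Sections 8.3.1 and 8.10.4 count 57 ± 4 days from the dose instead. The gaps are then 90 − 53 = 37, 90 − 57 = 33 and 90 − 61 = 29 days. The one-day difference in counting does not matter to the conclusion.

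**Notification against 90 days**

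Section 8.3.5 can be read in two ways.

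1. *Each man's own participation.* The first paragraph of Appendix 5, Section 2 supports this. Every man's reporting period ends at 57 ± 4 days after dosing, 29–37 days before day 90.
2. *The whole trial.* If the study runs to the last participant's last observation, men in earlier cohorts are covered for longer, by an amount that depends on how far apart the cohorts are dosed. Men dosed last gain nothing and keep the 29–37 day gap. In the last cohort the sentinel pair is dosed at least 3 days earlier, so their gap is at most 90 − (61 + 3) = 26 to 90 − (53 + 3) = 34 days.

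The last cohort is therefore short of 90 days on either reading. As planned it is the 5.4 mg/kg level, the highest dose, with at least 6 men on active drug.

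**How many men**

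Planned active: 4 + 4 + 6 + 6 + 6 = 26. Planned placebo: 5 × 2 = 10. Total 36. This is a ceiling for the contraception gap, because it matters only to men with a partner who could conceive or is pregnant, and pharmacologically only to those on active drug.

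**What else could capture a pregnancy after the visit**

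- Section 8.3.1 makes the Investigator report related SAEs, and other related events of concern, learned of at any time after discharge.
- The second paragraph of Appendix 5, Section 2 is open-ended.
- Appendix 5, Sections 3 and 4 class spontaneous abortions and birth defects as SAEs.

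Each depends on the Investigator learning of the event. None gives the participant a duty to report.

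**The case against.** The strongest reply has four parts.

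**The dates do not conflict.** A reader might infer that criterion 6 contradicts itself because its opening sentence ends at Day 57 ± 4. The text does not support that. The donation bullet gives its own dates, the specific term governs, and site staff can apply all three duties. This part of the reply stands.

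**The reason may be redacted.** A blacked-out block follows criterion 6 in both places, and much of the drug background, benefit/risk and dose justification is masked. It would be wrong to say that the sponsor has no rationale; only that none is readable. This stands too. A masked reason that separates donation from intercourse would answer the contraception half. It would not by itself explain why pregnancies conceived while the donation precaution still runs need not be reported.

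**The direction of the fix is a judgement.** With no readable half-life, semen or reproductive-toxicity result, the mismatch could mean a generous donation limit as easily as a short contraception limit. That is fair, and it keeps the severity low. Aligning upward is still the cautious choice in a first-in-human study, and it uses the sponsor's own number.

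**Notification is consistent and has backstops.** Contraception, AE reporting and pregnancy notification all use 57 ± 4 days, and the provisions listed above remain open after that. A reader might infer that later pregnancies would never be captured; that goes too far. But an uncomplicated pregnancy conceived after the window reaches the Investigator only by chance. The monthly recall of ADA-positive men keeps some in contact for longer, but neither moves the contraception date nor creates a duty to report.

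**Conclusion.** The point holds as a low-severity precautionary alignment. Contraception and pregnant-partner protection end 30–38 days before the donation limit (29–37 days if counted from dosing). The participant's duty to report a partner pregnancy ends 29–37 days before day 90 for men dosed last, and for every man if the period is read per participant.

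This rests on three things: the opening sentence of criterion 6 governing the two bullets without dates, the dose being single, and no redacted or consent text overriding the readable dates. A reader might infer that partners or embryos are at shown risk after Day 57. The documents contain nothing readable that would establish or quantify such a risk.

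**What to change.** - **Criterion 6, synopsis and Section 5.1:** run the contraception and pregnant-partner undertakings to 90 days after dosing, so that all three bullets share one end date.
- **Section 8.3.5 and the first paragraph of Appendix 5, Section 2:** set partner-pregnancy notification and collection to 90 days after dosing for every participant, whichever cohort he is in. Use the same date in the consent form.

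The cost is about one extra month of contraception for participants, plus protocol and consent wording. No extra visit is needed. The AE reporting period and the end-of-study definition stay as they are; a pregnancy reported after the final visit would be handled as post-study follow-up.

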5.2 EXCLUSION CRITERIA

Participants are excluded from the study if any of the following criteria apply:

Medical Conditions

1. Concomitant disease or condition that could interfere with, or treatment of which might interfere with, the conduct of the study, or that would, in the opinion of the Investigator, pose an unacceptable risk to the participant in this study.
2. History of any clinically significant gastrointestinal, renal, hepatic, broncho-pulmonary, neurological, psychiatric, cardiovascular, endocrinological, ophthalmologic, hematological or allergic disease, metabolic disorder, cancer or cirrhosis.
3. Any suspicion or history of alcohol abuse and/or suspicion of regular consumption of drug of abuse within the last 5 years.
4. Positive result on hepatitis B (HBV), hepatitis C (HCV), or human immunodeficient virus (HIV) 1 and 2.
5. [REDACTED]
6. [REDACTED]
7. History or presence of clinically significant ECG abnormalities [REDACTED]
[REDACTED]
8. Clinically significant abnormalities (as judged by the Investigator) [REDACTED]
[REDACTED]
9. Any major illness within one month before the screening examination or any febrile illness within one week prior to screening and up to first dose administration.
10. Impaired hepatic function as indicated by screening aspartate aminotransferase (AST) or alanine aminotransferase (ALT) $\geq 1.5 \times$ the upper limit of normal (ULN) or abnormal total bilirubin unless due to Gilbert's disease.
11. Any clinically relevant history of hypersensitivity or allergic reactions, either spontaneous or following drug administration, or exposure to foods or environmental agents.
12. History of hypersensitivity to biologic agents or any of the excipients in the formulation.
13. History of raised intra-cerebral pressure or vertebral joint pathology

[figure not shown]
Prior/Concomitant Therapy

14. Use of prohibited medication or herbal remedies as described in the section of concomitant medications
15. Prior administration of gantenerumab (RO4909832)
16. Any vaccination within two months prior to Day 1

Prior/Concurrent Clinical Study Experience

17. Participation in an investigational drug medicinal product or medical device study within 30 days before screening or within seven times the elimination half-life if known, whichever is longer.

23. Other Exclusions

18. Participants who regularly smoke more than 5 cigarettes daily or equivalent and are unable or unwilling not to smoke during the in-house period.
19. Donation or loss of blood over 500 mL within three months prior to Day 1 and donation of blood for the duration of the study until follow-up.
20. 
21. Claustrophobia, presence of pacemakers, aneurysm clips, artificial heart valves, ear implants, or foreign metal objects in the eyes, skin, or body that would contraindicate an MRI scan.
22. Inability or unwillingness to meet study requirements (see inclusion criteria).

